12.3 Planned Interim Analyses (if applicable)

No interim analyses are planned.

12.4 Final Analysis Plan

Analytic Samples. At the request of our DSMB, main outcomes will be analyzed using two analytic samples. One will include all 737 initially enrolled participants, regardless of study eligibility or study retention. Since no follow-up data is being collected on 19 of these individuals because they were ineligible and mistakenly enrolled, primary outcome data for these individuals will be treated as missing data. The second analytic sample (n = 718) will be limited to those individuals who were eligible to participate and included in the study. Analytic findings based on this second analytic sample will be considered the primary study results, but we will present the results from both analyses if results for the primary outcomes differ between the two samples. However, since missing data will be imputed as smokers and non-utilizers of dental care, and the 19 individuals not included in the primary analytic sample were equitably distributed across groups (9 vs. 10), we do not anticipate their exclusion will alter the primary findings. All analyses will use an ITT methodology such that subjects are analyzed according to their assigned treatment group, regardless of noncompliance, protocol deviation or withdrawal from treatment utilization.

Primary and secondary analyses. To assess the difference between the experimental and control groups for smoking abstinence, the regression model will include data from both follow-up time points in a single model to improve power and adjust for possible correlation within

individuals using generalized estimating equations.¹ To assess differences in dental care utilization, we will compute whether participants saw a dentist post-enrollment using data from each follow-up, then run a single logistic regression model. We will specify an independent working correlation structure and estimate robust standard errors to avoid making model assumptions about the variance. Models will use a logit link function for the binary primary outcomes and odds ratios will be used to quantify differences between groups. To improve precision and power, analyses will be adjusted for the following pre-specified baseline characteristics that are expected, based on prior knowledge, to be important predictors of outcome or missing data: sex, age, pharmacotherapy use (e.g., NRT), baseline cigarettes per day, depression history, self-efficacy, and motivation for quitting. Models will also adjust for variables used to stratify randomization (dental insurance coverage and state quitline).

To estimate the effects of the intervention on secondary outcomes (e.g., completing or scheduling a dental appointment, brushing, self-efficacy, motivation, etc.), we will apply similar regression models as described for the primary outcomes, using appropriate link functions dependent on outcome type, and further adjust for baseline outcome value when appropriate.

To handle missing follow-up data for the primary outcomes we will assume that missing subjects are smokers and are non-users of dental service. In sensitivity analyses, we will use modern imputation methods to impute missing outcome data, based on the observed pattern of missingness.² We also will conduct a respondent only missing data sensitivity analysis that only includes subjects with observed outcome data (i.e., a complete case analysis).

Mediation Analyses. If the enhanced UC is more effective than UC for either primary outcome at 6 months, we will then conduct mediator analyses to assess whether relevant secondary outcomes measured at 2 months (self-efficacy, motivation, knowledge,) mediate at least part of this effect. Mediation will be explored separately for each significant main outcome. These analyses will be conducted using the framework recommended by Baron and Kenny,⁴⁹ but using more recent statistical methods developed to better quantify and decompose different aspects of the mediation effect.⁵⁰ Having demonstrated the association between the intervention and the outcome variable (the “total effect” of the intervention on the outcome), the second step will be to demonstrate the association between the intervention and each mediator. We will construct a regression model for each mediator with the 2 month score of the mediator as the dependent variable and intervention indicator as independent variables. We will conduct this for each potential mediator and only include those mediators that have at least a $P < 0.10$ -level significant relationship with the intervention as potential mediators in the following step. The third step is to demonstrate the reduction of the intervention effect on the outcome after removing the effect of the mediator(s). We will construct a multi-mediator inverse probability weighted (IPW) regression model. This approach allows us to estimate the direct effect of intervention after rebalancing the intervention groups with respect to the mediators. The application of the IPW approach, as compared to the traditional approach of adjusting for multiple mediators, allows us to more appropriately account for confounding between a mediator and the outcome both

by additional mediators and by other measured variables. Further, we are better able to estimate the indirect effects of each mediator in a causal framework through decomposition of the total effect of intervention into indirect effects through each mediator and the direct effect after accounting for all mediators. Specifically, we will first model the probability of the intervention given the mediators (all mediators that were found associated with intervention in step 2) using logistic regression adjusting for potential baseline confounders. From this model we will obtain the estimated probabilities that each person received their observed intervention given their observed mediator value. We will then use an IPW regression to model the primary outcomes on intervention status while adjusting for the baseline level of the outcome and mediator and weighting out the effect of the mediator. Comparing the weighted to the unweighted model will allow us to estimate how much of the direct effect of intervention on the outcome can be explained by each potential mediator. We will further be able to quantify the amount of effect explained by each mediator independent of the other mediators.

Process Analyses. Summary statistics will be used to characterize quantitative acceptability ratings and scores. T-tests will be used to compare groups' on continuous ratings and chi-squares for proportions. Open-ended qualitative responses will be reviewed by investigators and may be transcribed and coded thematically, as needed to provide insight into the participants' satisfaction with the intervention programs and their components.

Economic Analyses. In addition to addressing the main scientific aims above, we will calculate the incremental cost of adding the Oral Health 4 Life program, from the perspective of a future payer, and produce a decision support tool that will allow quitline sponsors to determine whether, based on their own willingness to pay for quitline services, adding the Oral Health 4 Life program makes economic sense. This deliverable reflects quitline purchasers' concerns about program cost. The decision support tool will be created on a standard Excel spreadsheet and distributed at no cost to any individual or group wishing to assess the financial viability of adding the Oral Health 4 Life program to their quitline calls. The decision tool will have three components. The first is a detailed model of the cost associated with the oral health program. To generate this model component we will use activity accounting methods,⁵¹ which uses micro-costing to assign unit costs to every physical and human resource required to deliver an intervention or program. To micro-cost the additional cost of oral health counseling we will identify each resource required to add this component including development and training time, supplies, the additional time spent per call, etc. The second component of the decision tool is the probability of success for each positive outcome (cessation, dental visit, both) associated with a quitline program incorporating Oral Health 4 Life. This information will be based on trial results and we will incorporate uncertainty by using confidence intervals derived from the analyses of our trial data as described above. The third component will be a user entered factor based on their willingness to pay so that a potential sponsor of Oral Health 4 Life can assess, based on alternative assumptions about cost, programmatic success and

willingness to pay, whether investing in the Oral Health 4 Life program makes financial sense to them. Each user will have the ability to vary each model parameter to determine the circumstances under which they would be willing to invest in purchasing the Oral Health 4 Life program. Thus, each purchaser can decide for themselves what outcomes could be expected based on the amount they are willing to pay. This tool will be shared with quitline purchasers to inform individual decisions about whether the program provides sufficient perceived value to warrant program costs.

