7.3.2.5 Follow-up Assessments

Follow-up phone surveys will be conducted by the GHRI Survey Research Program at 2 and 6 months post-enrollment. Each participant will receive a reminder letter and text message approximately one week prior to their interview due date. Professional interviewers will then contact each person by phone to complete the standardized interview.

Persons who are reached by phone but who decline to participate in the full interview will be asked to provide information on each of the main outcomes of interest. Each

person who completes an interview (full or abbreviated) will be mailed a thank you letter and \$30 check or gift card as a thank you for their time.

During each follow-up contact, survey staff will confirm that the contact information on file is correct for each participant (mail address, cell phone number, home number, and email address).

Persons who cannot be reached within 2 weeks of their scheduled due date will be mailed a written survey to complete and return by mail. Persons who are not reached by phone and do not return the written survey within 4 weeks post-due date at 2 month follow-up or 6 weeks post-due date at 6 month follow-up will be coded as unable to reach. Other response options include: refused, deceased, and unknown.

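### The knowledge and attitude scores have no stated main-analysis method for missing data, and the planned model ignores the 2-month score when month 6 is missing. This costs some precision, and biases the arm contrast materially only if dropout relates to that score differently by arm.

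*Combined protocol and SAP*

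**What the plan says.** The analysis rules are in section 12.4.

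- **Model.** The plan states: "We will specify an independent working correlation structure", with robust standard errors. For abstinence, "the regression model will include data from both follow-up time points in a single model to improve power".
- **Extension to secondary outcomes.** For these, "we will apply similar regression models as described for the primary outcomes", with a link suited to the outcome type and adjustment for the baseline value where appropriate. Self-efficacy and motivation are named as examples. Knowledge is not named there, but section 3.2.2 lists its change to months 2 and 6 as a secondary outcome.
- **Main missing-data rule.** "To handle missing follow-up data for the primary outcomes we will assume that missing subjects are smokers and are non-users of dental service".
- **Sensitivity analyses.** The same paragraph continues: "In sensitivity analyses, we will use modern imputation methods to impute missing outcome data, based on the observed pattern of missingness". It then adds a respondent-only analysis. No secondary outcome is named.

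Section 12.2 claims complete follow-up by design for the primary outcomes only, because their gaps are filled in. Section 7.3.2.5 adds a source of gaps specific to the other scores: people who are reached by phone but "decline to participate in the full interview will be asked to provide information on each of the main outcomes of interest".

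**The concern.** For the primary outcomes, working independence does no harm, because every missing value is filled by rule. The knowledge and attitude scores differ. Counting a missing person as a smoker or non-user has no meaning on a knowledge scale or a 5-point item. An abbreviated interview can also supply the primary outcomes while leaving these scores blank, so they may be missing more often.

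With an independence working correlation and an arm effect for each time point, the 6-month contrast is a regression on 6-month respondents alone. The same person's 2-month score is probably the best available predictor of the missing value, and it goes unused. Section 12.1(c) sets a superiority hypothesis on these scores, so both precision and the validity of the contrast matter for a stated secondary objective.

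**Working it through.** **The plan's own figure.** No size or power figure is given for these scores. The abstinence calculation in Table 2 (12% v 21%, 90% power, two-sided 0.05, pooled variance) reproduces:

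n per arm = [1.960√(2×0.165×0.835) + 1.282√(0.12×0.88 + 0.21×0.79)]² / 0.09² = 355.4, so 356 per arm and 712 in total, as stated.

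It allows for no dropout, and that is justified for the primary outcomes only.

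**Inputs.** From the documents: n = 718, follow-up at 2 and 6 months, independence working correlation, baseline adjustment. Assumed, because the documents give none of them: 22-27% missing at month 6, SD 1, correlation of baseline with each follow-up 0.5, 2-to-6-month correlation r = 0.5 to 0.7, and the slope of dropout on the 2-month score.

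**Precision.** If dropout is unrelated to the scores, using the 2-month score cuts the variance by roughly (fraction missing) × (partial correlation of the 2- and 6-month scores given baseline)². The partial correlation is (r − 0.25)/0.75.

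- r = 0.5: 0.27 × 0.333² = 3.0%
- r = 0.6: 0.27 × 0.467² = 5.9%
- r = 0.7: 0.27 × 0.600² = 9.7%

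Simulation at r = 0.6-0.7 gave about 3-10%.

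**Bias.** Let d be the amount by which the mean 2-month score of an arm's 6-month respondents exceeds that of the whole arm. After baseline adjustment, that arm's 6-month mean is off by about (r − 0.5×0.5)d. The contrast is therefore off by about (r − 0.25)(d_enhanced − d_control). What matters is the difference in d between arms. Simulation with 1,000,000 subjects, and coverage from 2,000 trials of 718, gave the following.

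| Dropout depends on the 2-month score (log-odds per SD) | True effect | Contrast bias, r = 0.5 / 0.7 | 95% CI coverage, r = 0.5 / 0.7 |
|---|---|---|---|
| Not at all | 0.2 | +0.002 / −0.001 | 95% / 94% |
| Same in both arms, 0.5 | 0.2 | 0.000 / −0.004 | 93% / 94% |
| Same in both arms, 1 | 0.2 | −0.013 / −0.018 | 95% / 93% |
| Enhanced arm only, 0.5 | 0 | +0.029 / +0.055 | 92% / 89% |
| Enhanced arm only, 1 | 0.2 | +0.048 / +0.085 | 90% / 77% |
| Enhanced arm only, 1 | 0 | +0.056 / +0.105 | 88% / 71% |
| Opposite directions by arm, 0.5 | 0 | +0.063 / +0.115 | 86% / 69% |

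The formula agrees with the simulation at r = 0.7:

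- Enhanced arm only, slope 1, no effect: the raw enhanced-arm mean is off by 0.159, so d = 0.159/0.7 = 0.227, and 0.45 × 0.227 = 0.102 (simulated 0.105).
- Same slope of 1 in both arms, effect 0.2: the raw arm means are off by 0.160 and 0.132, so the difference in d is −0.028/0.7 = −0.040, and 0.45 × −0.040 = −0.018 (simulated −0.018).

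Using the 2-month score brought the contrast to within 0.005 SD of the truth in every row.

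A second simulation assumed about 73% response, r = 0.6-0.7 and a true effect of 0.25 SD. The planned estimate was 0.24-0.25 with equal slopes, 0.26-0.28 with moderately different slopes, and 0.29-0.33 with dependence in the enhanced arm only. A separate run of that last case reached 0.35. The likelihood estimate stayed at about 0.25.

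**Scale.** With 73% of 718 responding (524, or 262 per arm) and residual variance 1 − 0.5² = 0.75, the standard error is √(0.75 × 2/262) = 0.076 SD. A bias of 0.01-0.03 SD is 0.1-0.4 standard errors. A bias of 0.04-0.10 SD is 0.5-1.3.

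**The case against.** **The model is partly inferred.** Calling the models similar is not an explicit commitment to one two-time-point independence model, and section 12.4 describes pooling both follow-ups only for abstinence. That is fair. It changes little, because a separate 6-month regression would also rest on 6-month respondents alone.

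**Imputation is already planned.** The sensitivity sentence speaks of missing outcome data without repeating the word primary, and it follows the paragraph on secondary outcomes. A reader might infer either that these scores are covered or that they are certainly excluded. The text settles neither. Even on the generous reading it is a sensitivity analysis, so the main analysis of these scores still has no missing-data step.

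**Bias needs a particular pattern.** A reader might infer that any dependence of dropout on the 2-month score biases the treatment effect. The equal-slope rows show otherwise: each arm's observed mean shifts (by 0.06 to 0.16 SD), but the shifts nearly cancel. A reader might also infer that the programme's benefit will be overstated by 17-39% (0.293/0.25 to 0.347/0.25). That range needs dependence in the enhanced arm and none in control. The documents do not establish such a pattern, and its direction could be reversed. Interviewers are blinded and separate from the coaches, surveys are paid in both arms, and people who leave the intervention may stay in follow-up. On the other side, participants are unblinded and only one arm receives oral health contact, so an arm-specific pattern is plausible but undocumented.

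**Baseline adjustment helps.** It does, and it is included in the working. It removes only the part of the bias that baseline carries.

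**The remedy is not perfect.** Two-month scores will have gaps too. With 25% of them missing at random, a likelihood estimate kept a residual bias of about 0.01-0.02 SD.

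**Conclusion.** The point holds as a gap in the main analysis of the continuous secondary scores. The certain cost is modest: observed 2-month data are discarded, at about 3-10% of variance under the assumptions above. Bias in the arm contrast is conditional. It is about 0.01-0.02 SD or less if dropout relates to the 2-month score in the same way in both arms, about 0.01-0.03 SD if the relation differs moderately by arm, and about 0.04-0.10 SD (at r = 0.6-0.7) if it exists in one arm only. None of the quantities behind these figures is in the documents. The abstinence and dental-care results, the sample size, and the 2-month mediator scores used in the mediation analysis are unaffected. The change is still worth making, because it is cheap and removes dependence on an assumption that the plan does not state.

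**What to change.** In section 12.4, name the missing-data method for the continuous secondary scores. Either of these would do:

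1. A repeated-measures likelihood model with baseline score, the pre-specified covariates and stratification variables of section 12.4, arm, time and arm-by-time, an unstructured covariance for the two follow-ups and robust standard errors. It should use everyone with a score at either follow-up.
2. The planned GEE after multiple imputation done separately by arm, with the 2-month score and the same covariates in the imputation model.

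Keep the respondent-only analysis as a sensitivity analysis, and say whether the existing imputation sentence covers secondary outcomes. The binary outcomes can stay as planned.

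The cost is SAP wording only, with no new data and no change in sample size. The first option uses a working normal model for Likert-type scores. The second adds a little imputation work.

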3.2.2 Secondary

Secondary behavioral outcomes and process variables of interest are:

- **Smoking abstinence** assessed at 2 month follow-up (7 day point prevalent abstinence [PPA] with missing cases imputed). Additionally, we will assess abstinence at 2 and 6 months using a complete case (respondent only) analysis where missing data values are not imputed, to determine if imputation has a meaningful effect on the study results.
- We will assess whether groups differ in terms of the proportion of participants who either seek professional dental care following enrollment or have a future appointment scheduled at 6 months.
- Change in **oral health knowledge** from baseline to 2 and 6 month follow-up will be assessed using a scale adapted from Brennan et al⁴⁵ to address oral health behaviors (as opposed to tooth decay); include smoking, alcohol use, sugar free gum, and fruits and vegetables intake; and modify scripting for better phone delivery.
- Change in self-reported **self-efficacy** and **motivation** from baseline to 2 and 6 month follow-up. Self-efficacy and motivation will be assessed using a 5 point Likert-type scale.

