5 STUDY ENROLLMENT AND WITHDRAWAL

5.1 Subject Inclusion Criteria

In order to be eligible to participate in this study, a participant must meet all of the following criteria (see also Eligibility Screen in Appendix D):

- Male or female, aged 18 or older
- Eligible for multi-call services through a participating tobacco quitline [in Louisiana, Nebraska, or Oregon] managed by Alere Wellbeing
- Can read and speak in English
- Able to comfortably read small print (i.e., no significant visual impairments that limit ability to read the intervention materials)
- Current daily smoker and smokes at least 5 cigarettes a day
- Interested in quitting smoking in next 30 days
- Have some or all natural teeth
- Have not visited a dentist for a checkup or teeth cleaning in the past 6 months and do not have an appointment scheduled in the next 6 months
- Has a cell phone capable of receiving text messages and provides cell phone number
- Has internet access for personal use
- Willing to talk about ways to improve their oral health
- Provides verbal consent to participate

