12 STATISTICAL CONSIDERATIONS

12.1 Study Hypotheses

All hypotheses tested will be evaluations of superiority of the enhanced intervention (UC cessation counseling + oral health promotion program) compared to UC (UC cessation counseling). Null hypotheses assume that participants in the enhanced intervention group are equal to the participants in the UC group. We hypothesize that, compared to people in the UC arm, participants in the enhanced intervention will:

- a. Be more likely to quit smoking as evidenced by 7 day PPA rates at 6 month follow-up (primary outcome) and at 2 month follow-up (secondary outcome)
- b. Be more likely to see a dental care professional in the past 6 months at 6 month follow-up [primary outcome] or at least be more likely to seek dental care or have scheduled a future appointment [secondary outcome].
- c. Exhibit more positive change in relevant oral health knowledge/beliefs and attitudes (e.g., self-efficacy, motivation) that could influence future behavior change [secondary outcomes].

We hypothesize that positive change in participants' knowledge, attitudes, and beliefs at 2 months will mediate positive change in the primary outcome behaviors at 6 months; and that the Oral Health 4 Life program will be acceptable to quitline callers

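### The P<0.10 mediator screen in step 2 names no baseline score and so gives up power; separately, the baseline-outcome term in step 3 is constant and needs rewording

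*Combined protocol and SAP*

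**What the plan says.** **The hypothesis and the measures.** Section 12.1 hypothesises mediation through favourable change: "knowledge, attitudes, and beliefs at 2 months will mediate positive change in the primary outcome behaviors at 6 months". Section 3.2.2 describes oral health knowledge, self-efficacy and motivation as change, the last two "from baseline to 2 and 6 month follow-up. Self-efficacy and motivation will be assessed using a 5 point Likert-type scale". Baseline values of these scores are therefore available.

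**Step 2.** The Mediation Analyses paragraph of section 12.4 specifies, for each candidate, a "regression model for each mediator with the 2 month score of the mediator as the dependent variable and intervention indicator as independent variables". It will then "only include those mediators that have at least a $P < 0.10$ -level significant relationship with the intervention". Step 3 uses only the mediators that pass.

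**Step 3.** The weighted regression will "model the primary outcomes on intervention status while adjusting for the baseline level of the outcome and mediator".

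**Other models in section 12.4.** The paragraph on primary and secondary analyses adjusts for a listed set of baseline characteristics and for the two stratification factors (dental insurance and state quitline), and gives precision and power as the reason. For secondary outcomes, self-efficacy and motivation among them, it adds the baseline value of the outcome where appropriate.

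**Entry criteria.** Section 5.1 requires each participant to be a "Current daily smoker and smokes at least 5 cigarettes a day", with no dental checkup or cleaning in the previous 6 months. Section 12.2 takes this to mean that nobody will have seen a dentist in that period.

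**The concern.** Step 2 decides which mediators are studied at all, yet as written it is less precise than the models on either side of it. Without the baseline score, stable differences between people stay in the residual variance. A mediator that truly responds to the programme is then more likely to miss P<0.10. If it does, it never enters the weighting model, and whatever it carries is reported as part of the direct effect. The trial would understate how the programme works.

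In step 3, adjusting for the baseline outcome looks like a safeguard. For abstinence it cannot be one, because everyone enrolled smokes daily.

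**Working it through.** **The plan's own figure.** The documents give no calculation for the mediation analysis, so the only stated figure to reproduce is the sample size in section 12.2. With pooled variance, two-sided alpha 0.05, 90% power and 12% versus 21% (mean 0.165):

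n per arm = [1.960 × √(2 × 0.165 × 0.835) + 1.282 × √(0.12 × 0.88 + 0.21 × 0.79)]² / 0.09² = 355.4, rounded up to 356, or 712 in total.

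This matches, as do the other five rows of Table 2. The sample size is not in question.

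**Is the step 2 screen biased?** In 5,000 simulated trials of 718 people with complete data and a baseline-to-2-month correlation of 0.5:
- With a true standardised effect of 0.15, the mean arm difference was 0.149 on the 2-month score and 0.149 on the change score.
- With no effect, the unadjusted screen passed 10.1% of the time, in line with the nominal 10%.

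**What does it cost in power?** Inputs:
- Two-sided P<0.10 (section 12.4; two-sided is assumed), critical value 1.645.
- n = 718 (section 12.4, primary analytic sample, complete 2-month data) or n = 500 (assumed). A lower number is plausible because section 7.3.2.5 lets people who decline the full interview report only the main outcomes.
- Standardised effect d = 0.15 or 0.20, and correlation r = 0.3, 0.5 or 0.7. All are assumed.

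SE = √(4/n) × √(1 − r²), with r = 0 for the unadjusted model. Power = Φ(d/SE − 1.645); the other tail is negligible.

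Example with n = 500 and d = 0.15:
- Unadjusted: SE = 0.0894, d/SE = 1.677, Φ(0.032) = 51.3%.
- Adjusted, r = 0.5: SE = 0.0894 × 0.866 = 0.0775, d/SE = 1.936, Φ(0.292) = 61.5%.

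| n | d | Unadjusted | Adjusted, r = 0.3 | r = 0.5 | r = 0.7 |
|---|---|---|---|---|---|
| 500 | 0.15 | 51.3% | 54.5% | 61.5% | 75.9% |
| 500 | 0.20 | 72.3% | 75.8% | 82.6% | 93.1% |
| 718 | 0.15 | 64.2% | 67.8% | 75.0% | 87.9% |
| 718 | 0.20 | 85.0% | 87.8% | 92.6% | 98.2% |

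**Would a change score do instead?** Its SE is √(4/n) × √(2(1 − r)). With n = 718 and d = 0.15, power is 52% at r = 0.3, 64% at r = 0.5 and 83% at r = 0.7. That is worse than the unadjusted 2-month score at 0.3, equal to it at 0.5, and below baseline adjustment throughout.

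**The step 3 term.** Baseline 7-day abstinence is zero for every eligible participant (section 5.1). A design matrix with intercept, arm, baseline mediator and a constant baseline outcome has 4 columns and rank 3. The coefficient of the constant cannot be estimated, and dropping it leaves the intervention estimate unchanged.

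**The case against.** **Silence may not mean exclusion.** Section 12.4 calls the mediators secondary outcomes, and its rule for secondary outcomes already adjusts for baseline where appropriate. Step 2 speaks of independent variables in the plural. It could be shorthand for the adjusted models. This stands as an ambiguity. Step 2 sets out its own model, names one regressor and does not refer back, so an analyst following it literally would fit the unadjusted version.

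**Change hypothesised, raw score tested.** A reader might infer that the screen tests the wrong quantity. It does not: under randomisation the expected arm difference is the same on both scales. Nor does chance baseline imbalance make the screen invalid, because the nominal 10% error rate already allows for it. Both points reduce to lost power. Balance among 2-month respondents alone is not guaranteed, which is a further reason to adjust.

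**The gain may be small.** This stands at low correlation: at r = 0.3 it is about 3 to 4 percentage points in every row of the table.

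**The step 3 term does no harm.** This also stands. A reader might infer that step 3 is biased or has no useful baseline predictors. The documents do not support that. The outcome model includes the baseline mediator, the weight model adjusts for potential baseline confounders, and section 12.4 lists varying covariates for the primary-outcome models. The phrase may even be meant for something that varies, such as cigarettes per day. For dental care the constancy rests on the reading in section 12.2, since section 5.1 rules out only checkups and cleanings.

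**Conclusion.** The point holds as one of efficiency and clear wording. As written, step 2 omits a baseline covariate that is already collected. Across the assumed inputs (d of 0.15 or 0.20, r from 0.3 to 0.7, n of 500 or 718), adding it raises the chance that a true mediator passes by about 3 to 25 percentage points. The correlation drives most of that range, and none of these inputs is in the documents.

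The unadjusted screen is neither biased nor inflated under randomisation with complete 2-month data. The step 3 term is empty for abstinence and, on the reading in section 12.2, for dental care, but it does not distort the estimate.

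Severity is minor. Mediation is secondary and runs only if a primary outcome is significant. No primary comparison depends on it.

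**What to change.** Two sentences in the Mediation Analyses paragraph of section 12.4:

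1. **Step 2.** State that each 2-month mediator score is regressed on the intervention indicator, the baseline score of the same mediator and the two randomisation strata (dental insurance and state quitline). Do not use a bare change score.
2. **Step 3.** Replace the baseline level of the outcome with the baseline covariates already listed for the primary-outcome models in section 12.4. Keep the baseline mediator term, and use the same set in the weighted and unweighted models so that their comparison reflects the weighting alone.

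The cost is wording only. No new data, visits or participants are needed.
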